1.1 Background

Leber's Hereditary Optic Neuropathy

LHON is a maternally inherited loss of vision due to atrophy of the optic nerve. More than 90% of individuals with LHON harbour one of three point mutations in mitochondrial DNA (mtDNA) (G11778A, T14484C, G3460A) affecting genes encoding complex I subunits of the respiratory chain (Mackey 1996, Newman 2013). It typically presents in young adults, mostly men, as painless acute or subacute visual failure of both eyes in quick succession. The estimated prevalence is approximately 2.2 per 100,000 (Mascialino et al., 2012) and LHON is thus an Orphan Disease according to EU and US criteria. Clinically, the acute phase of the disease begins with blurring of central vision and colour de-saturation that affect both eyes. After the initial symptoms, both eyes are usually affected within two to four months from disease onset. Within 12 months of visual loss in one eye, over 97% of patients will have second eye involvement. The central visual acuity deteriorates to the level of counting fingers in up to 80% of cases. Following the nadir, acuity may improve. The degree of improvement is dependent, in part, also on the precise genetic mutation of affected patients. With disease progression, individuals then proceed into the atrophic phase and are usually legally blind for the rest of their lives with a permanent large centrocecal scotoma (Sadun et al., 2011).

Idebenone 2-(10-hydroxydecyl)-5,6-dimethoxy-3-methyl-cyclohexa-2,5-diene-1,4-dione has been suggested to be effective in by-passing the complex I deficiency resulting from the mtDNA point mutations and maintaining cellular energy production by stimulating the alternative pathway through complexes II and III (Haefeli et al., 2011). This activity may also reduce the production of reactive oxygen species (ROS) associated with complex I deficiency and to protect cell membranes and mitochondria from oxidative damage. This provides a strong rationale for its use in LHON (summarized in Gueven and Faldu, 2013; Gueven, 2014).

Detailed information on the medicinal product and on non-clinical data is available in the Investigator's Brochure (IB).

1.2 Rationale for the Study

The randomized, placebo-controlled RHODOS (SNT-II-003) trial (Klopstock et al., 2011), the retrospective cohort study of Carelli et al., (2011), Santhera's ongoing Expanded Access Program (EAP) and several case reports (summarized in Gueven and Faldu, 2013), provide evidence that idebenone promotes the recovery of VA in patients with LHON. However, due to the nature of these datasets, this evidence is not considered comprehensive.

In view of the urgent medical need and poor prognosis of LHON if untreated, a randomized, placebo-controlled study to provide comprehensive data is not considered feasible in LHON. An open-label study is therefore considered the most appropriate strategy for gathering additional evidence for the efficacy of idebenone in the treatment of LHON. The primary objective of this study is therefore to compare the outcomes for patients treated with idebenone ≤1 year of the onset of symptoms in this study with those of matching untreated patients from an external natural history control group generated in a historical case record survey (CRS).

In RHODOS, LHON patients enrolling up to 5 years after the onset of symptoms of disease were treated with idebenone. Whilst natural history VA outcomes data collected from LHON patients early in the course of the disease is available, relatively little reliable natural history VA outcomes data is available from patients with longer disease durations. The primary endpoint of this study will therefore compare the VA outcomes for patients treated with idebenone ≤1 year of the onset of symptoms with matching natural history control data. Secondary endpoints will include outcomes for patients treated with idebenone >1 year after the onset of symptoms. Since LHON

is known to lead to the apoptotic loss of retinal ganglion cells where the extent of loss increases with time since onset of disease, this study will explore further the relationship between time since onset at the initiation of idebenone therapy and CRR, where possible compared to untreated control patients.

The treatment duration in RHODOS was 6 months and a larger proportion of idebenone-treated patients presented with CRR in VA compared to placebo. However, data from Santhera's ongoing Expanded Access Program (EAP) indicates that prolonged treatment can increase both the proportions of patients with CRR of VA and the magnitude of the recovery observed.

Proportions of Patients and Eyes in the EAP with CRR from VA Nadir following 6 months and 12 months of treatment

CRR from Nadir	Patients		Eyes		Treatment duration at assessment [months]			
in the Efficacy Population	all	CRR	all	CRR	mean	(SD)	min	max
Patients with 6m assessment available	62	CRR at 6m 19 (30.6%)	124	CRR at 6m 30 (24.2%)	5.8	(1.0)	3.1	8.1
12m assessment available	47	CRR at 12m 17 (36.2%)	94	CRR at 12m 28 (29.8%)	11.6	(1.3)	9.1	13.9
at last observation	69	CRR at last obs. 34 (49.3%)	138	CRR at last obs. 55 (39.9%)	15.4	(9.0)	2.8	36.2

6m assessment : closest to 6 months, values at 3-9 months considered

12m assessment: closest to 12 months, values at 9-15months considered

Source Tables : EAP 01-01, EAP 01-02, EAP 01-03, EAP 02-01, EAP, 02-02, EAP 02-03

Magnitude of Recovery in Eyes in the EAP with CRR from VA Nadir at the 6 month, 12 month or at the last observation

Recovery* from Nadir [logMAR]**	N	mean	SD	median	max	min
at the 6 month vist	15	-0.47	0.31	-0.38	-1.00	-0.14
at the 12 month vist	15	-0.62	0.48	-0.40	-1.40	-0.10
at last observation (mean treat. dur. 20.9 m)	15	-0.93	0.42	-1.08	-1.44	-0.14

^{*}for eyes with CRR from BL where recovery had occured at the 6 months visit and a 12 month visit was available, too

Note, for these 15 eyes the VA at BL was also the VA at Nadir

Furthermore, data from the RHODOS and from the EAP provide evidence that the LHON-causative mutation harboured is prognostic of CRR in VA.

Therefore, secondary objectives of this study are to provide information on the effect of treatment duration on both the proportions of patients presenting with CRR and on the magnitude of any response with increasing treatment time and on the influence of the mutation harboured on CRR rate compared to spontaneous CRR (sCRR) untreated control patients.

The study will also allow the assessment of the safety and tolerability of long-term treatment with idebenone, with particular emphasis on the proportion of patients experiencing elevated Liver Function Tests (LFTs) or changes in blood cell counts.

^{**}off chart set to 1.70 [logMAR]

2 Study Objectives and Endpoints

2.1 Study Objectives

2.1.1 Primary Objective

 To assess efficacy of idebenone in the promotion of recovery or stabilization of visual acuity in patients treated with idebenone ≤1 year after the onset of symptoms, compared to an external natural history control group of idebenone naïve patients

2.1.2 Secondary Objectives

- To assess efficacy of idebenone in the promotion of recovery or stabilization of vision in LHON patients treated with idebenone >1 year after the onset of symptoms, compared to an external natural history control group of idebenone naive patients
- To compare the promotion of recovery or stabilization of visual acuity in LHON patients treated with idebenone ≤1 and >1 year after the onset of symptoms
- To assess the influence of mutation on the promotion of recovery or stabilization of visual acuity in LHON patients treated with idebenone
- To assess the influence of time since onset of symptoms prior to the initiation of treatment with idebenone on the promotion of recovery or stabilization of visual acuity in LHON patients
- To assess the influence of duration of treatment with idebenone on changes in visual acuity in LHON patients
- To assess safety of long-term treatment of LHON patients with idebenone.

2.2 Study Endpoints

2.2.1 Primary Endpoint

 Proportion of eyes with clinically relevant recovery of VA from Baseline or in which Baseline VA better than 1.0 logMAR was maintained at Month 12 in patients treated with idebenone ≤1 year after the onset of symptoms, compared to matching external natural history control group

Clinically Relevant Recovery (CRR) is defined as a change from "off-chart" visual acuity (VA) to at least 1.6 logMAR value or an improvement of at least 0.2 logMAR value within "on-chart".

2.2.2 Secondary Endpoints

- Components of the primary endpoint:
 - Proportion of eyes with CRR of VA from Baseline at Month 12 compared to matching external natural history control group
 - Proportion of eyes in which Baseline VA better than 1.0 logMAR was maintained at Month 12 compared to matching external natural history control group.
- Proportion of eyes in patients treated with idebenone >1 year after the onset of symptoms with CRR of VA from Baseline or in which Baseline VA better than 1.0 logMAR was maintained at Month 12 compared to external natural history control group, in all patients and classified by mutation
- Proportion of eyes and patients treated with idebenone ≤1 year after the onset of symptoms with CRR of VA from Baseline or in which Baseline visual acuity better than 1.0 logMAR was maintained following 6, 18 and 24 months of treatment with idebenone compared to matching external natural history control group, in all patients and classified by mutation

- Proportion of eyes/patients treated with idebenone ≤1 year or >1 year after the onset of symptoms with "Off-chart" VA at Baseline in whom VA improves to better than 1.60 logMAR by Month 6, 12, 18 and 24
- Proportion of eyes/patients treated with idebenone ≤1 year or >1 year after the onset of symptoms with VA in the categories of better than 1.0 logMAR, 1.0 to 1.68 logMAR and above 1.68 logMAR at each assessment time point up to Month 24
- Safety as assessed by AE count and laboratory analyses during the study

3 Study Design

3.1 Summary of Study Design

The study will be an open-label interventional study requiring 80 patients enrolled ≤1 year after the onset of symptoms to complete the 12 month treatment period (for evaluation of the primary endpoint), and 80 patients enrolled >1 year after the onset of symptoms to complete the 12 month treatment period (for evaluation of the secondary endpoints in these patients).

This multinational study is conducted with one protocol for sites under the IND (U.S. sites) in compliance with the IND requirements contained in 21 CFR 312, and a different version of the protocol for foreign sites not under the IND. As the intent is to pool the data from U.S. and foreign sites, it is ensured, as required, that the protocol versions are very similar or identical.

Patient eligibility for enrolment will be determined during the Baseline (Visit 1). Beginning at Baseline (Visit 1), the patient will receive study medication to take at home and will undergo regular assessments in the clinic throughout the study period until Visit 8 (Month 24) at which time the study medication is withdrawn. For all patients, there will be a final follow-up 28-35 days after study medication withdrawal. Patients enrolled in the study will commence study medication intake on the first day after the Baseline visit.

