idebenone therapy and CRR, where possible compared to untreated control patients.

The treatment duration in RHODOS was 6 months and a larger proportion of idebenone-treated patients presented with CRR in VA compared to placebo. However, data from Santhera's ongoing Expanded Access Program (EAP) indicates that prolonged treatment can increase both the proportions of patients with CRR of VA and the magnitude of the recovery observed. Furthermore, data from the RHODOS and from the EAP provide evidence that the LHON-causative mutation harboured is prognostic of CRR in VA. Therefore, secondary objectives of this study are to provide information on the effect of treatment duration on both the proportions of patients presenting with CRR and on the magnitude of any response with increasing treatment time and on the influence of the mutation harboured on CRR rate compared to spontaneous CRR (sCRR) in untreated control patients.

The study will also allow the assessment of the safety and tolerability of long-term treatment with idebenone, with particular emphasis on the proportion of patients experiencing elevated Liver Function Tests (LFTs) or changes in blood cell counts.

Number of Centres

Approximately 35

Multinational study with US sites operating under IND and EU sites not operating under IND.

Number of Patients

80 patients presenting ≤1 year after the onset of symptoms will be enrolled to ensure 61 provide VA assessments following 12 months of idebenone treatment (primary endpoint).

80 patients presenting >1 year after the onset of symptoms will be enrolled to ensure 61 provide VA assessments following 12 months of idebenone treatment (secondary endpoint). Patients will be stratified according to time since onset of symptoms with a maximum of 30 patients to be enrolled in any of the strata of >1 - \leq 2 years, >2 - \leq 3 years, >3 - \leq 4 years and >4 - \leq 5 years since onset of symptoms.

Inclusion Criteria

- 1. Impaired visual acuity in affected eyes due to LHON
- 2. No explanation for visual loss besides LHON
- 3. Age \geq 12 years
- 4. Onset of symptoms ≤5 years prior to Baseline
- 5. Confirmation of either G11778A, G3460A or T14484C LHON mtDNA (for the ITT population, not required for enrolment)
- 6. Written informed consent obtained from the patient
- 7. Ability and willingness to comply with study procedures and visits

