6.5.2 Procedures for Handling Discontinued Patients

Investigators should make every attempt to contact those patients who do not return for scheduled visits or follow-up.

Whenever a patient is withdrawn from the study, all efforts should be made to complete and report the observations as thoroughly as possible. A final evaluation must be completed for that patient, including all Follow-up Visit evaluations (see Section 6.5.1) if possible, and documenting the reasons why the patient was withdrawn from the trial.

Withdrawals due to intercurrent illnesses or AEs must be fully documented in the CRF with the addition of supplementary information if available and/or appropriate. Withdrawals due to non-attendance must be followed-up by the investigator to obtain the reason for non-attendance.

Information gathered should be described on the End of Study page of the CRF and on the appropriate forms (i.e., Adverse Events, Concomitant Medication).

Withdrawn patients will not be replaced.

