9.6 Sample Size and Power Considerations

The present study is designed to provide sufficient statistical power for a pre-planned indirect comparison of the primary endpoint against an external natural history control group.

As defined in the original LEROS study protocol (Version1.0, 29 January 2016, Section 9.6), the sample size calculation for LEROS assumed an expected 24% responder rate in the external natural history control group (combined data from SNT-IR-006 and SNT-CRS-002). The protocol defines a pre-planned check of the estimate of responder rate in the control group, once the enrolment of the new natural history study (SNT-CRS-002) has been completed. In case the responder rate in the control group is different from 24%, a sample size re-calculation using the updated control group estimate can be considered.

As SNT-CRS-002 study was completed, the data collected in the natural history studies has now been checked for the estimate of the responder rate. Based on the combined data from 175 eyes in the two natural history studies (SNT-IR-006 and SNT-CRS-002), the estimated responder rate is below 22%, i.e. lower than the initially expected rate of 24%. Although the determination of the exact responder rate for the natural history studies requires final data from the LEROS study for matching purposes, it is reasonable to assume that the responder rate of the natural history studies is not higher than 22%. The sample size for LEROS study is therefore re-calculated using the same methods as in the original protocol (Version1.0, 29 January 2016). In order to reach a power of 90% for the comparison of the responder rates between the natural history studies (assumed to be 22% instead of 24%) and the LEROS study (assumed to be 40%, as defined in the protocol), evaluable data from altogether 110 eyes from the LEROS study is required. In order to account for a drop-out rate of 30% (as defined in the protocol), at least 80 patients (equal to 160 eyes) will be enrolled to the LEROS study.

The sample size calculation was done with nQuery Advisor version 8.3.

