To assess efficacy of Raxone® in the promotion of recovery or stabilization of visual acuity in patients treated with Raxone data is compared to an external natural history control group of idebenone naïve patients (CRS-1 and CRS-2).

LEROS is a multi-country, multi-centre, open-label interventional study with 80 patients to be enrolled ≤ 1 year after the onset of symptoms to complete the 12 months treatment period (for evaluation of the primary endpoint), and 80 patients enrolled ≥ 1 year after the onset of symptoms to complete the 12 months treatment period.

Detailed study procedures and design is described in the described in the LEROS CSP.

CRS-1 is a multi-country, multi-centre, historical case record survey which collected historically documented VA data for all patients with a genetically confirmed diagnosis of LHON. No exclusion criteria were applied. Detailed study procedures and design is described in the CRS-1 CSP.

CRS-2 is a multi-country, multi-centre, historical case record survey which collected data on the VA of eligible patients from existing medical records. Detailed study procedures and design is described in the CRS-2 CSP.

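### Two printed Month 12 targets per group, 80 completing (Protocol 3.1) and 61 with visual acuity (Synopsis), disagree with the plan's own 30% drop-out, under which about 56 of 80 are expected

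*Protocol*

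**What the plan says.** - **Protocol 3.1** makes completion the requirement for the ≤1-year group: "requiring 80 patients enrolled ≤1 year after the onset of symptoms to complete the 12 month treatment period". For the other group it asks for "80 patients enrolled >1 year after the onset of symptoms to complete the 12 month treatment period".
- **Protocol Synopsis, Number of Patients**, makes 80 the number enrolled and 61 the number assessed: "80 patients presenting ≤1 year after the onset of symptoms will be enrolled to ensure 61 provide VA assessments" and, likewise, "80 patients presenting >1 year after the onset of symptoms will be enrolled to ensure 61 provide VA assessments".
- **Protocol 9.6**, repeated in **SAP 6**, requires 110 evaluable eyes for the ≤1-year comparison and enrols enough to "account for a drop-out rate of 30% (as defined in the protocol), at least 80 patients (equal to 160 eyes"). For the >1-year group it states only an aim to collect the same number of eyes, with no separate drop-out rate.
- **Protocol 6.5.2**: "Withdrawn patients will not be replaced".
- **SAP 5** has "80 patients to be enrolled ≤ 1 year after the onset of symptoms to complete the 12 months treatment period", in which 80 is attached to enrolment.

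Amendment History item 11 says that Section 3.1, Section 9.6 and the Synopsis were all updated for the same sample size re-calculation. The disagreement is therefore between current passages.

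**The concern.** For the same 80 patients, Section 3.1 read literally allows no loss, the Synopsis allows just under a quarter, and Section 9.6 allows 30%. These cannot all describe one plan.

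What is at stake is the yardstick for the trial's own target. If between 56 and 60 patients in the ≤1-year group gave Month 12 data, the trial would meet Section 9.6, miss the Synopsis figure and fall well short of Section 3.1. Protocol 10.10 lists insufficient recruitment as a possible reason for terminating the study, so the recruitment target should have one meaning. The >1-year group is affected too, because the Synopsis and Section 3.1 repeat 61 and 80 for it.

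**Working it through.** **Inputs.** 80 enrolled (Synopsis, 9.6); 30% drop-out and 110 evaluable eyes (9.6, SAP 6); no replacement (6.5.2); 61 assessed (Synopsis); 80 completing (3.1). Assumption: two evaluable eyes per patient, as 9.6 implies by equating 80 patients with 160 eyes.

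**Step 1. Reproduce the enrolment figure in 9.6.** 110 / 2 = 55 patients. 55 / (1 − 0.30) = 78.6, so 79, which the plan rounds up to 80.

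**Step 2. Reproduce the 110 eyes.** The test compares 22% with 40% at two-sided 0.05, with pooled variance and no continuity correction. Section 9.6 does not state the number of control eyes used, so the 175 eyes behind its 22% estimate are assumed. Then 110 treated eyes give 89.9% power, which matches the stated 90% to rounding. Equal group sizes would need 137 eyes per group, so the match depends on the 175. Eyes are treated as independent.

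**Step 3. Expected yield from 80 enrolled.** 80 × 0.70 = 56 patients, or 112 eyes. On the Step 2 basis 112 eyes give 90.2% power.

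**Step 4. Loss and enrolment implied by each figure.**

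| Source | Patients at Month 12 | Loss implied from 80 | Enrolment needed at 30% loss |
|---|---|---|---|
| 9.6 | 55 required (110 eyes) | up to 31.25% (1 − 55/80) | 79, rounded to 80 |
| Synopsis | 61 | at most 23.75% (1 − 61/80) | 61/0.70 = 87.1, so 88 |
| 3.1 | 80 | 0% | 80/0.70 = 114.3, so 115 |

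The expected 56 is 5 below the Synopsis figure and 24 below the Section 3.1 figure.

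**Step 5. How well 61 is assured.** With X ~ Binomial(80, 0.70), P(X ≥ 61) = 0.135.

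**Possible origin of the 61.** Inflating by multiplication gives 61 × 1.3 = 79.3, rounded up to 80. Dividing by 0.70 gives 88. The documents do not say how 61 was obtained, so this is only a conjecture.

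**The case against.** The best defence is that 80 is an enrolment number throughout and Section 3.1 merely phrases it awkwardly. The Synopsis, Section 9.6, SAP 5, SAP 6 and amendment item 11 all treat 80 as enrolled. This is probably what was meant, and it is why SAP 5 needs only clarification. It does not rescue Section 3.1 as written, which makes completion by 80 the requirement, and it leaves the 61 unexplained.

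A second argument is that the quantities differ: completing treatment, giving a visual acuity assessment, and evaluable eyes. Protocol 9.4.2 admits an assessment at 12±3 months, so a patient who leaves after the Month 9 visit could still count. The distinction is fair. However, Section 9.6 applies its 30% directly to evaluable eyes, so 80 × 0.70 is already the number expected to be evaluable, and no passage uses the distinction to reach 61.

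A third is that 30% is a planning allowance, and that Section 9.6 and SAP 6 say at least 80, so enrolment is not capped. This stands. A reader might infer that 61 cannot be delivered. The documents do not support that: 61 is reached if loss is 23.75% or less, or if more patients are enrolled. What fails is the Synopsis claim that 80 enrolled secures 61.

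Finally, no passage ties the end of enrolment, or a reported shortfall, to 61 or to 80 completers. The primary analysis uses the eyes that have Month 12 data, and the SAP takes precedence and contains no 61. This limits the practical consequence to an unclear target.

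**Conclusion.** The inconsistency is real: two printed targets do not follow from the stated drop-out rate and the no-replacement rule. It should be corrected, but it does not damage the inference. Three stronger readings should be set aside.

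- **Three printed completer counts.** Only 80 and 61 are printed. The 56 is derived here from 80 and 30%.
- **An underpowered trial.** Section 9.6 is internally consistent, and the expected number of eyes exceeds its requirement. Neither the analysis set nor the type I error changes.
- **The same contradiction in both groups.** The 30% and the 110 eyes are stated for the ≤1-year comparison. The >1-year group takes them over only through the aim of the same number of eyes.

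The 13.5% assumes a true loss of exactly 30%, independent between patients, and exactly 80 enrolled. A lower loss or higher enrolment would raise it.

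**What to change.** Align the Synopsis and Protocol 3.1 with Section 9.6, and clarify SAP 5.

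- **≤1-year group:** at least 80 patients enrolled; withdrawn patients not replaced; about 56 patients (112 eyes) expected with Month 12 visual acuity at 30% drop-out; 110 eyes required.
- **>1-year group:** at least 80 patients enrolled, aiming for the same number of eyes.
- **Synopsis:** remove the 61 for both groups, or state the drop-out rate behind it and reconcile that rate with 30%.
- **Protocol 3.1:** reword so that 80 is the number enrolled and not the number required to complete 12 months.
- **SAP 5:** make plain that 80 is an enrolment number.

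The cost is wording in three places. No patients are added and no analysis changes. If the 61 is removed, the stated Month 12 yield becomes less favourable, at about 56.
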